7.6.1.7 Potential Drug-Induced Liver Injury

Wherever possible, timely confirmation of initial liver-related laboratory abnormalities should occur prior to reporting a potential drug-induced liver injury (DILI) event ([FDA 2009](#)). All occurrences of potential DILIs, meeting the defined criteria, must be reported as SAEs.

Potential drug-induced liver injury is defined as:

- ALT or AST elevation > 3 times (3X) upper limit of normal (ULN); AND
- Total bilirubin > 2X ULN, without initial findings of cholestasis (elevated serum alkaline phosphatase), AND
- No other immediately apparent possible causes of aminotransferase (AT) elevation and hyperbilirubinemia, including, but not limited to, viral hepatitis, pre-existing chronic or acute liver disease or tumor(s), or the administration of other drug(s) known to be hepatotoxic

In general, an increase of serum AT to > 3X ULN should be followed by repeat testing within 48-72 hours of all four of the usual serum measures (ALT, AST, alkaline phosphatase, and total bilirubin) to confirm the abnormalities and to determine if they are increasing or decreasing.

Inquiry regarding symptoms should also be made (e.g., fatigue, nausea, vomiting, right upper quadrant pain or tenderness, fever, rash). Subjects may be retested locally, but normal laboratory ranges should be recorded and results made available to the investigator immediately for review. All data must be recorded on the case report forms. Close observation should be initiated if symptoms persist or repeat testing shows AT >3xULN for subjects with normal baseline

measures or 2-fold increases above baseline values for subjects with elevated values before drug exposure. If close monitoring is not possible, study drug should be discontinued.

Close observation includes:

- Repeating liver enzyme and serum bilirubin tests two or three times weekly. Frequency of retesting can decrease to once a week or less if abnormalities stabilize or the study drug has been discontinued and the subject is asymptomatic.
- Obtaining a more detailed history of symptoms and prior or concurrent diseases.
- Obtaining a history of concomitant drug use (including non-prescription medications and herbal and dietary supplement preparations), alcohol use, recreational drug use, and special diets.
- Ruling out acute viral hepatitis types A, B, C, D, and E; autoimmune or alcoholic hepatitis; NASH; hypoxic/ischemic hepatopathy; and biliary tract disease.

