7.6.4 Clinical Laboratory Tests

Laboratory assessments will be performed to evaluate safety at scheduled time points (see Appendix 12.1) during the course of the study. The following assessments will be performed at the local laboratory:

- Complete Blood Count, including white blood cell count with five-part differential (neutrophils, lymphocytes, monocytes, eosinophils, and basophils), red blood cell count, platelet count, hemoglobin, and hematocrit.
- Chemistry panel, including electrolytes (sodium, potassium, chloride, and carbon dioxide), creatinine, blood urea nitrogen (BUN), estimated glomerular filtration rate, glucose, albumin, total protein, liver function tests (total and direct bilirubin, ALT, AST, alkaline phosphatase, lactate dehydrogenase), amylase, and lipase.
- Coagulation tests, including prothrombin time (PT), partial thromboplastin time (PTT), and international normalized ratio (INR).
- Urinalysis, including dipstick results for color, appearance, specific gravity, pH, glucose, bilirubin, ketones, occult blood, and protein; as well as spot protein and creatinine.
- Hepatitis B and C tests include Hep B surface antigen (HBsAg), Hep B surface antibody (HBsAb), Hep B core antibody (HBcAb) and hepatitis C virus (HCV) antibody. Results that may be consistent with chronic or active infection, and/or subjects with known prior active hepatitis B or C infection, should undergo PCR tests for Hep B and/or C, respectively.
- Pregnancy test, consisting of blood or urine testing for beta-human chorionic gonadotropin (β -hCG).

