7.7.2 Laboratory Tests

Clinical laboratory assessments for this study include: hematology, blood chemistry and liver function tests (LFT). Most hematology, blood chemistry and LFT parameters will be graded according to NCI-CTCAE version 4.03, as applicable. Numeric values will be analyzed after conversion into standard international units, where applicable. A complete listing of all laboratory parameters with normal ranges in standard international units is included in Appendix 5. Laboratory values with grade 3 or above will be listed. For subjects with grade 3 or higher values, all values of that lab test will be listed.

Continuous clinical laboratory results will be summarized by analyte and by visit after conversion into standardized SI results. Summary statistics for the change from baseline to end-of-treatment (EOT), where end-of-treatment will be summarized using the last non-missing post-baseline result no more than 45 days after treatment discontinuation or initiation of subsequent therapy (whichever is first, if applicable), will be tabulated. The largest change from baseline (increase or decrease) will be summarized in a shift table based on the CTCAE grade which will include both scheduled and unscheduled visits.

Laboratory-based summaries will be provided as follows:

- Observed, change from baseline, and percent change from baseline at each scheduled visit and EOT in parameter results

- Shift from baseline to maximum post-baseline CTCAE grade for hematology laboratory results
- Shift from baseline to maximum post-baseline CTCAE grade for chemistry laboratory results
- Elevations in AST, ALT, total bilirubin, and alkaline phosphatase as outlined in the FDA Guidance for Industry pertaining to premarketing clinical evaluations for drug-induced liver injury (DILI):
 - Elevations of AST, ALT, and either ALT or AST: 3x-, 5x-, 10x-, and 20xULN
 - Elevations of bilirubin defined as total bilirubin >2 xULN
 - Elevations of alkaline phosphatase >1.5 xULN
 - Elevations of ALT or AST (>3 xULN) accompanied by elevated total bilirubin (>1.5 xULN, >2 xULN)

In addition, a listing of potential Hy's Law cases (i.e., subjects with AST or ALT >3 xULN in combination with bilirubin >2 xULN) will be also presented. Results from unscheduled or repeated assessments will be included in the DILI evaluations, with elevations of AST or ALT in combination with total bilirubin at the same unscheduled or repeat assessment.

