32) Serosal Fluid entails procurement, where feasible, of any pericardial, pleural and/or ascitic fluid collected as part of routine care (e.g. as part of a therapeutic thoracentesis, pericardiocentesis, or paracentesis), for possible pharmacokinetic, pharmacodynamic and/or biomarker testing.

C. RANDOMIZATION ALGORITHM

Not Applicable

D. SAS ROUTINES

Endpoint	Test	SAS Code
ORR, CBR	95% Exact confidence interval for the proportion calculated using the exact binomial method	[REDACTED]
PFS, OS,	Kaplan-Meier method and 95% confidence interval for median calculated using the complementary log-log transformation	[REDACTED]

E. POTENTIALLY CLINICALLY SIGNIFICANT LABORATORY VALUES CRITERIA

No potentially clinically significant lab values criteria except the ones identified in section 7.6.2 were identified. The following normal ranges were used to identify values classified as High or Low.

Laboratory Test	Standard Result Unit	Normal Range Low	Normal Range High
Albumin	g/dL	3.5	5
Alkaline Phosphatase	U/L	30	120
ALT (SGPT)	U/L	10	40
AST (SGOT)	U/L	10	30
Basophils	10 ⁹ /L	0	0.2
Total Bilirubin	mg/dL	0.292	1.228
Blasts	%	0	0
Blood Urea Nitrogen	mmol/L	2.9	8.2
Calcium	mg/dL	8.2	10.2
Chloride	mmol/L	96	106
Carbon Dioxide	mmol/L	20	28
Serum Creatinine	mg/dL	0.6	1.2
Eosinophils	10 ⁹ /L	0	0.45
Glucose	mg/dL	70	110
Hematocrit	%	41	50
Hemoglobin	g/dL	14	17.5
Potassium	mmol/L	3.5	5
Lactate Dehydrogenase	U/L	100	200
Lymphocytes	10 ⁹ /L	1	4.8
Monocytes	10 ⁹ /L	0	0.8
Neutrophils	10 ⁹ /L	1.8	7.8
Platelets	10 ⁹ /L	150	350
Total Protein	g/dL	6	8
Sodium	mmol/L	136	142
WBC	10 ⁹ /L	4.5	11

F. ADVERSE EVENTS OF SPECIAL

Specific treatment-emergent adverse events of special interest (AESI) will be identified by the following search criteria:

Adverse Event of Special Interest

MedDRA Search Criteria / Codes

G. PLANNED TABLES, FIGURES AND LISTINGS

Table of Contents

TABLE 14.1_1.1 Disposition

TABLE 14.1_1.2 Analysis Populations

TABLE 14.1_1.3 Protocol Deviations

TABLE 14.1_2.1 Demographic Characteristics

TABLE 14.1_2.2 Baseline Characteristics

TABLE 14.1_2.3.1 Disease History

TABLE 14.1_2.3.2 Prior Therapies

TABLE 14.1_2.3.3 Medical History by System Organ Class and Preferred Term

TABLE 14.1_3.1 Treatment Exposure During Initial Treatment

TABLE 14.1_3.2 Dose Modification During Initial Treatment

TABLE 14.2_1.1 Best Response During Initial Treatment

TABLE 14.2_1.2.1 Best Response During Initial Treatment by Current Line of Therapy of 3L and 3L+

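### SAP Appendix E flags laboratory values High or Low against one fixed range for all subjects, although tests are run at local laboratories in both sexes, and the SAP names no other source for LLN or ULN

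*SAP*

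**What the plan says.** Appendix E of the SAP introduces its table with "The following normal ranges were used to identify values classified as High or Low". The columns are "Laboratory Test Standard Result Unit Normal Range Low Normal Range High"; there is none for sex, age or laboratory. Relevant rows are "Hemoglobin g/dL 14 17.5", "Hematocrit % 41 50" and "AST (SGOT) U/L 10 30". The ALT row runs from 10 to 40 U/L, and total bilirubin has an upper limit of 1.228 mg/dL.

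SAP 7.7.2 converts results to common units but gives no rule for relating a result to the range of the laboratory that produced it. On ranges it says only: "A complete listing of all laboratory parameters with normal ranges in standard international units is included in Appendix 5". The SAP's appendices are lettered, and Appendix E is the only list of normal ranges among them. The same section plans CTCAE v4.03 grading and shift tables, liver tables at 3x, 5x, 10x and 20x ULN, and a listing of potential Hy's Law cases (AST or ALT above 3x ULN with bilirubin above 2x ULN).

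Protocol 7.6.4 says of the safety laboratory tests: "The following assessments will be performed at the local laboratory". Protocol 9.2.9.3 plans listings with out-of-range flags, and shift tables measured against the standard normal range of the laboratory. Protocol 7.6.1.7, on local retesting after raised liver enzymes, asks that "normal laboratory ranges should be recorded and results made available to the investigator immediately for review".

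**The concern.** A fixed range suits a central laboratory with one set of methods. Here results come from many local laboratories, and Appendix E sets each laboratory's own limits aside for flagging. It also gives women and men the same haemoglobin and haematocrit limits. A value that the reporting laboratory calls normal can be listed as Low or High, and the reverse can also happen. A normal-range shift table of the kind in protocol 9.2.9.3 would then miss a change in a subject who is already flagged Low at baseline.

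The liver outputs matter more. If the ULN in 7.7.2 is the Appendix E ULN, the tables and the Hy's Law listing can disagree, in either direction, with the investigator's local reading. That reading presumably drives eligibility and the reporting of potential drug-induced liver injury as an SAE.

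**Working it through.** The plan states no figure to reproduce. The check is arithmetic on the Appendix E limits, with local limits assumed over a range because the documents give none.

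**1. Thresholds if Appendix E supplies the ULN** (multiple × listed ULN)

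- AST (ULN 30): 3x = 90, 5x = 150, 10x = 300, 20x = 600 U/L
- ALT (ULN 40): 3x = 120, 5x = 200, 10x = 400, 20x = 800 U/L
- Total bilirubin (ULN 1.228): 1.5x = 1.842, 2x = 2.456 mg/dL
- Alkaline phosphatase (ULN 120): 1.5x = 180 U/L

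**2. AST: local reading against the fixed reading.** Inclusion criterion 9e caps ALT and AST at 2.5x ULN (5x with hepatic involvement). I assume sites apply it with their own ULN, L. The Appendix E multiple is the AST value divided by 30.

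| Assumed L (U/L) | 3 × L | as multiple of 30 | 2.5 × L | as multiple of 30 |
|---|---|---|---|---|
| 30 | 90 | 3.00 | 75 | 2.50 |
| 35 | 105 | 3.50 | 87.5 | 2.92 |
| 40 | 120 | 4.00 | 100 | 3.33 |
| 45 | 135 | 4.50 | 112.5 | 3.75 |
| 50 | 150 | 5.00 | 125 | 4.17 |

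A subject at the 2.5x cap passes the fixed >3x line when 2.5 × L > 90, that is, when L > 36 U/L. With L = 40, an AST of 100 U/L is 2.5x locally and 100/30 = 3.33x under Appendix E.

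**3. The error can go the other way.** With an assumed local ALT ULN of 30, 3x local is 90 U/L, which is 90/40 = 2.25x under Appendix E, so a local >3x value just above 90 would be missed. With a local ULN of 60, 3x local is 180 U/L, or 4.5x. For bilirubin, an assumed local ULN of 1.0 mg/dL puts 2x local at 2.0 mg/dL, which is 2.0/1.228 = 1.63x; a local ULN of 1.5 gives 3.0/1.228 = 2.44x.

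**4. Haemoglobin flags.** For an assumed local LLN for women of 11.5 to 13 g/dL, every value from that LLN up to 14 is normal locally but Low under Appendix E. The band is 14 − 11.5 = 2.5 g/dL wide at one end and 14 − 13 = 1.0 g/dL at the other. With an LLN of 12, a fall from 13 to 11 g/dL is Normal-to-Low locally and Low-to-Low under Appendix E.

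**5. How far grades can move.** In the protocol's CTCAE extract (Appendix 12.5), LLN sets only the upper edge of Grade 1 for albumin, neutrophils and platelets; higher grades do not use it. A wrong LLN can therefore move these tests only between Grade 0 and Grade 1. Haemoglobin is not in the extract, so its grading cannot be checked from the documents. Multiples of ULN, by contrast, can move at any level.

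**The case against.** The strongest reply is that Appendix E ties its ranges to High and Low flags and nothing else. No text says they replace local limits for CTCAE grades, ULN multiples or the Hy's Law listing. The list that 7.7.2 calls Appendix 5 is described as complete and in SI units. Appendix E has no limits for coagulation, amylase, lipase or direct bilirubin, and gives several tests in g/dL or mg/dL. Protocol 9.2.9.3 can be read as meaning each laboratory's own range. This stands as far as it goes: the reach beyond flags is an inference. It is still the likely one, because E is the fifth appendix, it is the only list of ranges, and a programmer is given no other LLN or ULN.

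Several stronger readings are tempting but not supported:

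- **That all LLN- or ULN-based grades are wrong.** Only values between the two limits change, and step 5 confines the LLN effect in the extract to Grade 0 versus Grade 1.
- **That comparisons by gender are distorted.** The planned gender tables all concern adverse events as reported by investigators. Under protocol 7.6.1.1 and 7.6.1.6, a laboratory result becomes an adverse event on criteria such as clinical significance or need for treatment, not on an Appendix E flag. No laboratory table is listed by gender.
- **That the haemoglobin limits are men's limits.** The documents give no sex-specific ranges; they show only that women have no separate limits.
- **That a known share of women is misflagged.** With an assumed female LLN of 12, SD of 1.5 and mean of 11.5 to 13 g/dL, 32% to 50% of women would lie between 12 and 14. None of those inputs comes from this trial.

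Two further points stand. The SAP's listed laboratory shift tables are by CTCAE grade, so the Low-to-Low example bites only if the normal-range shift table in the protocol is produced. The request in protocol 7.6.1.7 to record ranges covers liver retests, not all laboratory data.

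**Conclusion.** The point holds for the High and Low flags: the rule is stated, it ignores sex and laboratory, and it can misclassify any value between the fixed and the local limit. For Grade 0 versus Grade 1 calls, the ULN-multiple tables and the Hy's Law listing, the effect is probable but rests on reading Appendix E as the source that 7.7.2 intends. If that reading is right, the liver categories are the most exposed, and the 36 U/L crossover for AST shows that a modest difference in local ULN is enough. How many subjects are affected cannot be worked out from the documents.

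The safety analysis is descriptive, with no formal inference, and ORR and OS are untouched. Nothing in the protocol's eligibility or liver-injury rules refers to Appendix E. This is a correction worth making because it is cheap and concerns hepatic safety displays; it is not a threat to the trial's main conclusions.

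**What to change.** In SAP 7.7.2 and Appendix E, state that High and Low flags, any CTCAE grade that depends on LLN or ULN, and all ULN-multiple categories, including the Hy's Law listing, use the reporting laboratory's own range for that sample, sex-specific where the laboratory has one. Keep Appendix E only as a fallback when the local range is missing, with separate male and female limits for haemoglobin, haematocrit and creatinine, and mark results for which it was used.

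Correct the cross-references at the same time. SAP 7.7.2 points to Appendix 5, and Appendix E points to section 7.6.2, which is Clinical Benefit Rate; laboratory tests are in 7.7.2. Settle the units, and state the limits for coagulation, since a coagulation grade-shift table (14.4_3.2) is planned.

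The cost is SAP wording, programming and some cleaning of range data. First confirm that local ranges are captured for all laboratory tests and not only for liver retests; if they are not, they must be collected from the sites. Design, visits and dosing do not change.

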APPENDIX 16.2_1.1 Disposition

APPENDIX 16.2_1.2 Enrollment

APPENDIX 16.2_1.3 Deaths

APPENDIX 16.2_2.1 Protocol Deviations

APPENDIX 16.2_3.1 Demography

APPENDIX 16.2_3.1.1 Demography of Subjects in Retreatment 1

APPENDIX 16.2_3.1.2 Demography of Subjects in Retreatment 2

APPENDIX 16.2_4.1 Malignancy History and Paraneoplastic Symptoms

APPENDIX 16.2_4.2 Medical History

APPENDIX 16.2_4.3 Prior Cancer Therapy

APPENDIX 16.2_4.4 Prior Cancer Radiation Therapy

APPENDIX 16.2_4.5 Surgeries and Procedures

APPENDIX 16.2_5.1 Study Treatment During Initial Treatment

APPENDIX 16.2_6.1.1 Target, Non-Target, and New Lesions by Investigator During Initial Treatment

APPENDIX 16.2_6.1.2 Target, Non-Target, and New Lesions by IRC During Initial Treatment

APPENDIX 16.2_6.1.2.1 Target, Non-Target, and New Lesions by IRC for Subjects in Retreatment 1

APPENDIX 16.2_6.1.2.2 Target, Non-Target, and New Lesions by IRC for Subjects in Retreatment 2

APPENDIX 16.2_6.2.1 Response Assessment by Investigator

APPENDIX 16.2_6.2.2 Response Assessment by IRC

APPENDIX 16.2_6.2.1.1 Response Assessment by Investigator for Subjects in Retreatment 1

APPENDIX 16.2_6.2.2.1 Response Assessment by IRC for Subjects in Retreatment 1

APPENDIX 16.2_6.2.1.2 Response Assessment by Investigator for Subjects in Retreatment 2

APPENDIX 16.2_6.2.2.2 Response Assessment by IRC for Subjects in Retreatment 2

APPENDIX 16.2_6.3 Objective Response and Clinical Benefit During Initial Treatment

APPENDIX 16.2_6.4 Time to Event and Key Subgroups

APPENDIX 16.2_7.1 Treatment-Emergent Adverse Events

APPENDIX 16.2_7.2 Treatment-Emergent Serious Adverse Events

APPENDIX 16.2_7.3 Treatment-Emergent Adverse Events Leading to Study Drug Withdrawal

APPENDIX 16.2_7.4 Fatal Treatment-Emergent Adverse Events

APPENDIX 16.2_7.5 Pre-Treatment or Post-Treatment Adverse Events

APPENDIX 16.2_7.6 Treatment Emergent Adverse Events of Subjects in Retreatment 1

APPENDIX 16.2_7.7 Treatment Emergent Adverse Events of Subjects in Retreatment 2

APPENDIX 16.2_8.1 Potential Hy's Law Cases During Initial Treatment

APPENDIX 16.2_8.2.1 Laboratory Results: Hematology

APPENDIX 16.2_8.2.2 Laboratory Results with CTCAE Grade 3 or Higher: Hematology

APPENDIX 16.2_8.3.1 Laboratory Results: Chemistry

APPENDIX 16.2_8.3.2 Laboratory Results with CTCAE Grade 3 or Higher: Chemistry

APPENDIX 16.2_8.4 Laboratory Results: Urinalysis

APPENDIX 16.2_8.5.1 Total Ab, ADC, and SC-DR002 Concentration

APPENDIX 16.2_8.6.1 Vital Signs

APPENDIX 16.2_8.6.2.1 Electrocardiogram

APPENDIX 16.2_8.6.2.2 Electrocardiogram: QTcF

APPENDIX 16.2_8.6.3 ECOG Performance Status

APPENDIX 16.2_8.6.4 Echocardiogram

